### 5.1.3. Immunogenicity Visit Windows

For the immunogenicity analysis, assessments will be allocated to an analysis visit based on the planned visit as captured in the CRF. Visits that are out of the protocol-defined visit windows (see the table below) will not be included in the per-protocol immunogenicity analysis. However, they may be included in sensitivity analyses.

**Table 4 – Immunogenicity timepoints**

Analysis time point label (Relative to Day 1)	Reference day	Target day (from reference day)	Window of target day (days)
Cohorts 1 and 2			
Day 1	Day of vaccination 1	1	(-∞, 1]
Day 15	Day of vaccination 1	15	[12, 18]
Day 29	Day of vaccination 1	29	[22, 36]
Day 85	Day of vaccination 1	85	[78, 92]
Day 183	Day of vaccination 1	183	[169, 197]
Day 365	Day of vaccination 1	365	[335, 395]
Day 730	Day of vaccination 1	730	[700, 760]
Day 1095	Day of vaccination 1	1095	[1065, 1125]
Cohorts 3 (Arms 10 and 13)			
Day 1	Day of vaccination 1	1	(-∞, 1]

Day 15	Day of vaccination 1	15	[12, 18]
Day 29	Day of vaccination 1	29	[22, 36]
Day 85	Day of vaccination 1	85	[78, 92]
Day 183	Day of vaccination 1	183	[169, 197]
Day 365	Day of vaccination 1	365	[335, 395]
Cohorts Cohort 3 (Arms 11a, 11b and 12) and Cohort 4			
Day 1	Day of vaccination 1	1	$(-\infty, 1]$
Day 15	Day of vaccination 1	15	[12, 18]
Day 29	Day of vaccination 1	29	[22, 36]
Day 85	Day of vaccination 1	85	[78, 92]
Day 183	Day of vaccination 1	183	[169, 197]
Day X	Day of vaccination 1	X	[X-30, X+30]
Day X+14	Day of vaccination 2*	15	[12, 18]
Day X+28	Day of vaccination 2*	29	[22, 36]
Day X+84	Day of vaccination 2*	85	[78, 92]
Day X+182	Day of vaccination 2*	183	[169, 197]
Day 730	Day of vaccination 1	730	[700, 760]
Day 1095	Day of vaccination 1	1095	[1065, 1125]
Day 1460	Day of vaccination 1	1460	[1430, 1490]
Day 1825	Day of vaccination 1	1825	[1795, 1855]

Notes: \* in case of missed vaccination 2, the actual date of missed vaccination 2 (i.e. the date of the day X visit) is used as a reference day.

## 5.2. Participant Dispositions

Participant information will be shown for the FAS. The number of participants in the following disposition categories will be summarized throughout the study by intervention group and overall:

- participants screened
- participants not randomized and not vaccinated
- participants not randomized and vaccinated
- participants randomized and not vaccinated
- participants randomized and vaccinated
- participants in the FAS
- participants in the PPI Set
- participants who discontinued study vaccine with reasons for discontinuation
- participants who discontinued the study with reasons for discontinuation

Also, the number of participants and percentage per phase will be tabulated.

Other participant information variables: demographics and baseline characteristics, major protocol deviations, and prior and concomitant medications will be analyzed as described in Sections 6.3, 6.4 and 6.5, respectively. Medical history and concomitant diseases will be tabulated by body system class and preferred term.

### 5.3. Primary Endpoint(s) Analysis

#### 5.3.1. Definition of Endpoints

For cohort 1 to 3 the primary safety endpoints are defined as:

- Serious adverse events (SAEs) and adverse events of special interest (AESIs) from first dose administration until 6 months after vaccination
- Solicited local and systemic adverse events (AEs) for 7 days after vaccine administration
- Unsolicited AEs from the time of vaccine administration through the following 28 days

In addition, for cohorts 1 and 2, and cohort 4 the primary immunogenicity endpoint is defined as RSV neutralization antibody titers.

#### 5.3.2. Analysis Methods for the Primary Safety endpoints

No formal statistical testing of safety data is planned. Safety data will be analyzed descriptively by cohort (or pooled over cohorts, as applicable) and study arm, and by group (cohort 1), as applicable, per phase and across the entire study period. All safety analyses will be made on the FAS.

The verbatim terms used in the eCRF by investigators to identify AEs will be coded using the Medical Dictionary for Regulatory Activities (MedDRA). Any AE occurring at or after the first vaccination is considered to be treatment emergent. All reported AEs with onset during the active phase (ie, AEs occurring after vaccination up to 28 days post-vaccination) or AEs present before the active phase but worsening during the active phase, and all SAEs, AEs leading to study or vaccine discontinuation during the study, potential AESIs and AESIs (up to 6 months after vaccination) will be included in the analysis. For each AE, the percentage of participants who experience at least 1 occurrence of the given event will be summarized. All other unsolicited adverse events collected outside the 28-day period will be presented through listings.

AESIs (as determined in Section 5.3.2.1) will be reported until 6 months post vaccination and additionally by different time periods:

- 0 – 28 days post dose,
- 29 days – 56 days post dose,
- 0 – 56 days post dose,
- 57 days – 6 months post dose,
- 0 – 6 months post-dose.

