| 
 
To assess the safety and reactogenicity of the selected RSV.preF-based vaccine formulation (based on Cohort 1 and 2 results), compared to the formulation to be used for future clinical development
 
 | 
 
SAEs and AESIs from first administration until 6 months after the last vaccination
 
Solicited local and systemic AEs for 7 days after each vaccine administration
 
Unsolicited AEs from the time of each vaccine administration through the following 28 days
 
 |
| SECONDARY                                                                                                                                                                                                                                       |                                                                                                                                                                                                                                                                                                                                 |
| 
 
To assess immune responses to the selected RSV.preF-based vaccine formulation (based on Cohort 1 and 2 results), compared to the formulation to be used for future clinical development
 
              | 
 
RSV neutralization antibody titers
 
                                                                                                                                                                                                                                            |
| 
 
To assess the durability of the immune response to the selected RSV.preF-based vaccine formulation in groups with and without revaccination
 
                                                          | 
 
RSV neutralization antibody titers
 
                                                                                                                                                                                                                                            |

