### Expanded Safety Cohort (Cohort 3)

In the expanded safety cohort, approximately 400 participants will be randomized in parallel to 1 of 5 arms (in a 6:3:3:2:2 ratio to Arms 10, 11a, 11b, 12, and 13; [Table 7](#)). No pauses in enrollment for safety assessments are planned. Participants will receive either the selected 2×1 mL formulation based on the results from Cohorts 1 and 2, the selected 1 mL formulation for future clinical development, placebo, or the current Ad26/protein preF RSV vaccine (1×10^11 vp Ad26.RSV-A.preF/150 µg RSV-A preF protein).

Vaccine components evaluated in Cohorts 1 and 2 will be administered as 2 IM injections of 1 mL in the same deltoid muscle. However, once the optimal composition is selected, manufacturing formulation will be adjusted to ensure the administration of a single 1 mL vaccine dose in subsequent cohorts. Participants in Arms 11a and 11b will receive the selected vaccine in a 1 mL formulation and a second injection with placebo (1 mL) for blinding purposes. Cohort 3 thus will compare the 2×1 mL formulation of the selected combination of RSV vaccine components from Cohorts 1 and 2 (Arm 10) with the 1 mL formulation to be used for future clinical development (Arms 11a and 11b) with follow-up for 1 year post-vaccination in a double-blind placebo-controlled fashion. Participants in Arm 13 will receive the current Ad26/protein preF RSV vaccine (1×10^11 vp Ad26.RSV-A.preF/150 µg RSV-A preF protein) in a 1 mL formulation and a second injection with placebo (1 mL) for blinding purposes. Participants in Arms 11a, 11b and 12 will continue the study to assess durability and the effect of revaccination with follow-up up to 5 years post first vaccination. The timing of revaccination (at least 12 months relative to the first dose) will be based on Ad26/protein preF RSV vaccine clinical data.

For a subset of the participants, additional cellular immunogenicity assessments will be performed. This subset will be referred to as the Cellular Immuno Subset and will consist of approximately 240 participants: 40 participants per arm in Arms 10, 12 and 13, and 60 participants per arm in Arms 11a and 11b. The Cellular Immuno Subset will be recruited in study sites that have PBMC collection capability.

VAC18195 (JNJ 64400141/ JNJ 64213175/ JNJ-86051823/ JNJ 78991172)

Clinical Protocol VAC18195RSV1001 Original

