### 9.2.3. Expanded Safety Cohort (Cohort 3)

The expanded safety cohort (Cohort 3) should provide sufficient safety data on the selected vaccine formulation to support late-stage development if the immunogenicity results of Cohort 2 are satisfactory.

Table 15 shows the probabilities of observing at least one AE in the expanded safety cohort with 150 participants per vaccine formulation, 50 participants receiving placebo, and 50 participants receiving  $1 \times 10^{11}$  vp Ad26.RSV-A.preF/ 150 µg RSV-A preF protein, at given true AE rates. This table shows that the current numbers give a reasonable probability to also observe less frequent events in the active arms in this cohort. Combining the 60 participants from Cohorts 1 and 2 and 150 participants from Cohort 3 for the selected vaccine formulation results in 210 participants for this formulation.

**Table 15: Probability of Observing at Least One Adverse Event in the Expanded Safety Cohort (Cohort 3) at a Given True Adverse Event Rate**

| True AE Rate (%) | Probability of Observing at Least One AE in N Participants (%) |        |        |        |
|------------------|----------------------------------------------------------------|--------|--------|--------|
|                  | N=50                                                           | N=60   | N=150  | N=210  |
| 0.5              | 22.2%                                                          | 26.0%  | 52.9%  | 65.1%  |
| 1                | 39.5%                                                          | 45.3%  | 77.9%  | 87.9%  |
| 2.5              | 71.8%                                                          | 78.1%  | 97.8%  | 99.5%  |
| 10               | 99.5%                                                          | 99.8%  | 100.0% | 100.0% |
| 25               | 100.0%                                                         | 100.0% | 100.0% | 100.0% |
| 50               | 100.0%                                                         | 100.0% | 100.0% | 100.0% |

AE = adverse event; N = number of participants.

The observation of 0 events (eg, SAEs) is associated with 95% confidence that the true event rate is below the rates specified in Table 16 for the considered number of participants.

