### **5.3.2.2. Analysis of Adverse Events**

Number and percentage of participants with at least one particular AE (unsolicited/solicited) will be tabulated. Unsolicited AEs will be summarized by System Organ Class (SOC) and Preferred Term (PT).

Solicited AEs will be summarized by class (administration site, systemic) and Derived Term. The number and percentages of participants with at least one solicited local (at injection site) or systemic adverse event will be presented. For solicited AEs, the following tables will be provided: overall summary, by worst severity grade, at least grade 3, related (systemic only), time to onset (in days) and duration (in days). Note: Duration is defined as number of days from the start of the event until resolution of the event. The time to first onset is defined as date of first onset – reference date + 1. The reference date is the start date of the post-dose period. For solicited AEs, the denominator for the percentages is the number of participants with solicited event data assessed by the investigator in the considered population, phase and arm (incidence per 100 participants/phase).

A tabulation of the distribution of temperatures per half degree intervals will also be provided.

Frequencies of unsolicited AEs, separately for all and vaccination-related only, will be presented by SOC and PT. The following tables will be provided: overall summary, all AEs, most frequent AEs, AEs with at least grade 3, related AEs, AEs leading to death, AEs leading to study discontinuation, SAEs, related SAEs, potential AESIs and AESIs, COVID-19 related AEs.

AESIs, AEs flagged by the investigator as potential AESI and AESIs identified via a programmed selection will be summarized by Interest Category and PT. Denominator for the percentages is the number of participants in the considered population, phase and arm (incidence per 100 participants/phase).

Potential AESIs selected programmatically will be tabulated by categories: ‘Embolic and thrombotic events (SMQ)’ and ‘Haematopoietic Thrombocytopenias (SMQ) (broad) or HLT = Thrombocytopenias’. Potential AESI determined programmatically, related to study vaccine (investigator assessment), will be tabulated similarly.

Potential AESIs as identified by the investigator, will be tabulated by categories: ‘Embolic and thrombotic events (SMQ)’ and ‘Haematopoietic Thrombocytopenias (SMQ) (broad) or HLT =

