#### 5.3.3. Analysis Methods for the Primary Immunogenicity endpoint(s)

For Cohort 1, 2 and 4 the primary endpoint will be RSV neutralization antibody titers measured for RSV-A and RSV-B. In Cohort 3, RSV neutralization antibody titers are a secondary endpoint.

Data of corresponding arms from Cohort 1 and Cohort 2 will be combined in all analyses. Immunogenicity data of corresponding arms from Cohort 3 and Cohort 4 will be combined as applicable, too.

Descriptive statistics will be used for all arms to analyze the actual values (geometric mean, 95% CI, minimum, maximum, median and quartiles) and fold increase from baseline at all timepoints, as well as the percentage of participants with 2- and 4-fold increases from baseline. Additionally, the RSV-A/RSV-B antibody ratio will be reported by time points and the fold increase of RSV-A/RSV-B antibody ratio from baselines will be calculated at all timepoints.

For combined data from Cohort 1 and Cohort 2, geometric mean ratios for each active arm relatively to control Arm 1a and relatively to control Arm 1b, as well as relatively to each other will be calculated at all available timepoints along with corresponding 95% CI as applicable.

For Cohort 3, Arms 11a and 11b will be combined and the active arms (10, 11a+11b, 13) will be compared to each other at all available timepoints up to 1 year after vaccination on Day 1 by calculating the geometric mean ratios along with corresponding 95% CIs.

For durability and revaccination evaluation analyses, the following arms will be combined and compared to each other for all timepoints:

- Arm 11a (Cohort 3) combined with Arm 14 (Cohort 4);
- Arm 11b (Cohort 3) combined with Arm 15 (Cohort 4);
- Arm 12 (Cohort 3) combined with Arm 16 (Cohort 4).

Geometric means per arm of values for RSV-A, RSV-B and the ratio of RSV-A/RSV-B, geometric mean ratios for RSV-A, RSV-B and the ratio of RSV-A/RSV-B between all active arms along with corresponding 95% CIs will be estimated via an analysis of variance (ANOVA) using log-transformed post-vaccination immuno parameter response as dependent variable and study arm as independent variable. The means and differences in mean and CIs will be back transformed (by exponentiation) to CIs around a geometric mean or geometric mean ratio. This analysis will be performed by time points, separately per parameter. As a sensitivity analysis, the ANOVA may also be performed adjusting for baseline titer, age and sex.

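### Cohort 3's primary objective compares the safety of two formulations, but the SAP pre-specifies only within-arm percentages, with no between-formulation difference or interval

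*SAP*

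**What the plan says.** Protocol section 3 gives Cohort 3 one primary objective: the safety and reactogenicity of the formulation selected from Cohorts 1 and 2, "compared to the formulation to be used for future clinical development". Protocol 4.1 identifies the contrast as Arm 10 (2×1 mL) against Arms 11a and 11b (1 mL plus a placebo injection to keep the blind), with randomisation "in a 6:3:3:2:2 ratio to Arms 10, 11a, 11b, 12, and 13". Protocol 9.2.3 counts participants "in the expanded safety cohort with 150 participants per vaccine formulation", which is only true if Arms 11a and 11b are taken together.

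The safety analysis is descriptive, without formal testing, on the Full Analysis Set, by cohort and study arm and by phase (SAP 5.3.2). The summary measure in that section is: "For each AE, the percentage of participants who experience at least 1 occurrence of the given event will be summarized". SAP 5.3.2.2 adds: "Number and percentage of participants with at least one particular AE (unsolicited/solicited) will be tabulated". It lists tables by worst grade, Grade 3 or higher, relatedness, time to onset and duration. The denominators it describes are per population, phase and arm. Protocol 9.4.4 says essentially the same.

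For neutralising titres, SAP 5.3.3 pools Arms 11a and 11b and compares Arms 10, 11a+11b and 13 "by calculating the geometric mean ratios along with corresponding 95% CIs". In Cohort 3 these titres are a secondary endpoint.

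**The concern.** The randomised contrast in Cohort 3 has a specified estimator and interval for a secondary endpoint but none for the primary one. The primary question would be answered by setting percentages side by side, with no statement of which differences the data rule out. The 150-person comparator is also not assured. Pooling over cohorts, which SAP 5.3.2 allows, is not the same as pooling Arms 11a and 11b, so the tables could show 150, 75 and 75.

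At stake is how the result is described. Similar percentages could be reported as similar tolerability although a difference of several points, or for common reactions about ten, remains possible. A visible gap could be reported as worse tolerability although it is compatible with none. Protocol 9.2.3 expects Cohort 3 safety data to support late-stage development, so the wording will be read closely.

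**Working it through.** **Inputs.** About 400 participants allocated 6:3:3:2:2 (Protocol 4.1). The ratio sums to 16, so Arm 10 has 400 × 6/16 = 150, and Arms 11a and 11b have 400 × 3/16 = 75 each; 75 + 75 = 150.

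**The plan's own figures.** Protocol 9.2.3 bases the size on "probabilities of observing at least one AE in the expanded safety cohort" and on the upper limit when no event is seen.

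- Chance of at least one event, 1 − (1 − p)^N, at N = 150: 52.9% for p = 0.5%, 77.9% for 1%, 97.8% for 2.5%. These match Table 15.
- One-sided 95% upper limit with zero events, 1 − 0.05^(1/150) = 1.98%. This matches the 2.0% in Table 16.

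These figures are correct, but each describes one group. None describes the difference between formulations.

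**Precision of the difference.** The documents give no expected event rates, so a range is assumed, with the same observed rate p in both groups. The Wald half-width is 1.96 × √[p(1 − p)(1/n₁ + 1/n₂)]. At p = 50% with 150 v 150 this is 1.96 × √(0.25 × 2/150) = 1.96 × 0.0577 = 11.3 points. The Newcombe column combines Wilson score limits for each group.

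| Assumed rate in both groups | Events, 150 v 150 | Wald, points | Newcombe, points |
|---|---|---|---|
| 50% | 75 v 75 | ±11.3 | ±11.2 |
| 30% | 45 v 45 | ±10.4 | ±10.3 |
| 20% | 30 v 30 | ±9.1 | ±9.1 |
| 10% | 15 v 15 | ±6.8 | ±7.0 |
| 2% | 3 v 3 | ±3.2 | ±3.9 |
| 0% | 0 v 0 | ±0.0 | ±2.5 |

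The Miettinen-Nurminen score interval gives ±11.3 at 50%, ±10.3 at 30% and ±7.0 at 10%. The last row shows why a score-type interval is needed: with no events, Wald has zero width.

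**When the observed rates differ, 150 v 150.**

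- 75 v 90 events (50% v 60%): difference 10 points, score 95% CI −1.3 to +21.1.
- 45 v 60 events (30% v 40%): difference 10 points, Newcombe 95% CI −0.8 to +20.5.
- 3 v 9 events (2% v 6%): difference 4 points, score 95% CI −0.5 to +9.2.

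**If Arms 11a and 11b are left separate (150 v 75).** Here 1/150 + 1/75 = 0.02. The Wald half-width at 50% is 1.96 × √(0.25 × 0.02) = 13.9 points; at 30% it is 12.7 and at 10% it is 8.3.

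**The case against.** The strongest reply is that the plan does what it declares. Both documents state that no hypothesis is tested and that data are analysed descriptively. Cohort 3 was sized on single-group figures, and those reproduce. There is no margin or safety decision rule, and in a Phase 1/2a study the absence of risk differences contradicts no stated method. This stands, so the point is not an error. It does not remove the case for an interval, because the titre analyses are equally descriptive and have one.

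Table specifications are deferred to a data presentation specifications document (SAP section 1), which could add a difference column. That cannot be excluded, but the SAP names no method for one.

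Four stronger readings are tempting, and the documents do not support them:

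- A reader might infer that the primary comparison can never be estimated. Counts and percentages per arm will be tabulated, so a difference and its interval can be derived afterwards. What is missing is pre-specification.
- A reader might extend the point to Cohorts 1 and 2, with safety judged against Arm 1b. The safety objective there is not worded as a comparison, and the Arm 1b contrast in Protocol 9.2.2 and 9.4.3 and in SAP 5.3.3 concerns immune responses. Safety does feed formulation selection, but no section names Arm 1b as its comparator.
- A reader might infer that equal percentages always leave more than 10 points open. That holds only for common events: the half-width is 9.1 points at 20% and passes 10 by 30%.
- A reader might infer that a progression decision turns on this contrast. No section makes Cohort 4 or later development depend on it. Protocol 4.1 already plans the single 1 mL dose for later cohorts.

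**Conclusion.** The point holds for Cohort 3. Its primary objective is comparative, yet no between-formulation safety measure or interval is pre-specified, and the pooling that forms the 1 mL group is stated only for immunogenicity. At 150 v 150, equal observed percentages leave about ±11 points open at a 50% rate, ±10 at 30% and ±7 at 10%. Without pooling, each contrast with Arm 10 widens to about ±14, ±13 and ±8. These sizes rest on assumed event rates, full enrolment and data from every participant; missing diary data would widen them. This is a cheap improvement: it changes what can be said about the primary comparison, not the design, size or conduct of the trial.

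**What to change.** In SAP 5.3.2.2:

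1. State that Arms 11a and 11b are pooled for safety after dose 1, up to the second vaccination. Arm 10 receives no second vaccination, and Arms 11a and 11b diverge from that point.
2. For Arm 10 v Arms 11a+11b, report the risk difference with a Miettinen-Nurminen 95% CI for: any solicited local AE; any solicited systemic AE; any solicited AE of Grade 3 or higher; any unsolicited AE to 28 days; and SAEs and AESIs to 6 months after dose 1. Revaccination is at least 12 months after dose 1, so the 6-month window is the same for both formulations.
3. Label the intervals descriptive and unadjusted for multiplicity, with no hypothesis test and no margin, and use them when describing the Cohort 3 primary comparison.

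No safety contrasts against Arm 1b need be added for Cohorts 1 and 2.

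The cost is a short SAP edit and some extra table columns on data already collected. The downside is a few more descriptive intervals to present.
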